Thoracic abdominal aortic aneurysms and perirenal abdominal aortic aneurysms currently face difficulties in clinical treatment methods due to the involvement of multiple veisceral branching vessels. Traditional treatments include open and hybrid surgery. Open surgery includes the Etheredge, Debakey, and Debakey-Schumacker methods, have risks of peroperative bleeding, shock, multiple organ failure etc. due to thoraco-abdorminal combined incision, sizabale wound, its and complex reconstraction of visceral artery. The prognoss of patients undergoing open surgeries is heavily dependent on the proficiency of surgical technique among operating surgeons.In order to prevent the potential risks of open surgery and reduce the size of the incision wound caused by traditional thoracotomy and laparotomy procedures, many scholars have made corresponding attempts. In 1999, Quiñones-Baldrich et al^[3] first used hybrid surgery for the treatment of TAAA^[3]. Even though hybrid surgery generates less surgical trauma than open surgery, the issues of high mortality and complications remain unsolved. Simultaneously, due to the increased exposure of complicated anatomical posterior peritoneal regions, hybridization techniques need to be performed by experienced vascular surgeons and high level treatment center, further limiting its clinical application.

In recent years, with the rapid development of endovascular therapy technology, current major endovaslcular treatments include fenestrated endograft, branched endograft, and octopus stents^[4,8]. The results of a crossestional study of 2,607 patients showed perioperative mortality rate of 23.9%, 30.9%, and 10.6%, respectively, and found that postoperative complications of endovascular therapy (10.5%) were significantly lower than those of open surgery (33.5%) and hybrid surgery (31.6%). In Comparison with open surgery and hybrid surgery, endovascular therapy has the following advantages: (1) minimally invasive surgery, no chest or abdominal incision; (2) There is no need to block aorta during operation, therefore reduce the occurrence of complications of visceral ischemia; (3) Reduce blood loss and hospitalization time; (4) Reduce spinal cord complications and the mid-stent patency rate is good. Endovascular therapy is being used in the treatment of thoracic abdominal aortic aneurysms due to its advantages such as small incision wound and low complication rate. However, the technique of interventional operation and the design of standardized branch stents are still the focus of the research, and further research is needed.

2. Study Design

2.1 Study Purpose

To evaluate the feasibility of the thoracic-abdominal aortic stent-graft system for endovascular treatment of thoracic-abdominal aortic aneurysms and pararenal abdominal aortic aneurysm.

2.2. Method Selection and Reasons

There are no commercially available stent-graft systems for the effective endovascular treatment for thoracoabdominal aortic aneurysms and pararenal abdominal aortic aneurysm in China, so a prospective, single-group feasibility study is proposed for this study.

2.3 Inclusion and Exclusion Criteria

2.3.1 Inclusion criteria

- (1) Age ≥ 18 and ≤ 80 years;
- (2) Patients diagnosed with type Crawford I-V thoracoabdominal aortic aneurysmsa and pararenal abdominal aortic aneurysm, and should meet at least one of the following conditions:
 - a) The maximum diameter of thoracoabdominal aortic aneurysms and

pararenal abdorminal aortic aneurysm > 50 mm;

- b) Rapid growth of sac >5 mm in diameter in the most recent 6 months;
- c) Definite symptoms of abdominal pain and low back pain associated with thoracicabdominal aortic aneurysms.
- (3) Patients with four indispensable reno-visceral arteries including superior mesenteric artery, celiac trunk and bilaterial renal arteries.
- (4) Proximal landing zone 20 36 mm in diameter;
- (5) Proximal landing zone ≥ 25 mm in length;
- (6) If distal landing zone in abdominal aorta, distal landing zone should be 12-36mm in diameter and ≥15 mm in length.
- (7) The visceral vascular branches landing zone 6~13 mm in diameter and ≥15 mm in length;
- (8) The renal artery landing zone 4.5~9 mm in diameter and ≥ 15 mm in length;
- (9) Patients who using the abdominal aortic bifurcation stent graft system should also meet the following criteria:
 - a. The iliac artery landing zone 7 ~25 mm in diameter;
 - b. The iliac artery landing zone ≥ 15 mm in length;
- (10) Patients with appropriate iliacofemoral access and at least one patent upper extremity access;
- (11) Patients who can understand the purpose of the trial, volunntarily participate and sign the informed consent form, and are willing to complete the follow-up according to the requirements of the protocol;

2.3.2 Exclusion criteria

- (1) Ruptured aortic aneurysm in unstable haemodynamic condition;
- (2) Aneurysmal aortic dissection;
- (3) Infected or mycotic aortic aneurysm;
- (4) Requiring simultaneous coverage or embolisation for bilateral internal iliac arteries;
- (5) Severe stenosis, calcification, or mural thrombus at stent-graft landing zone;
- (6) Diagnosis of acute coronary syndrome within 6 months;
- (7) Patients with any transient ischemic attack (TIA) or ischemic stroke within 3 months;
- (8) An allergic history for contrast agents, anticoagulants, antiplatelet drugs, stent graft or materials of delivery system#
- (9) Patients with connective tissue diseases;

- (10) Patients with takayasu arteritis;
- (11) Patients with serious vital organ dysfunction or other serious disease;
- (12) Preoperative liver renal function abnormalities (ALT or AST ≥ 5 times the upper limit of normal value), or serum creatinine ≥ 150 µmol/L;
- (13) Severe pulmonary insufficiency who cannot tolerate general anaesthesia;
- (14) Severe coagulation dysfunction;
- (15) Undergone major surgical or interventionic surgery within 30 days before surgery;
- (16) Patients whose systemic or local infection may increase the risk of intravascular graft infection;
- (17) Planning pregnancy, pregnancy, or breastfeeding;
- (18) The patient participated in other clinical trials or not completed or withdrawn from other clinical trials within the last 3 months at the time of screening period;
- (19) Life expectancy less than 1 year;
- (20) Patients not appropriate for endovascular repair based on the investigators' clinical judgement.

2.3.3 Exit criteria

All patients should participate in the study voluntarily, and may withdraw from the study at any time without penalty, and the rights and interests will not be affected thereby, and the reasons for discontinuing the study may include, but are not limited to:

- Patient voluntary withdrawal
- For therapeutic reasons, the investigator may allow the patient to withdraw from the study without patient's consent
- Patient lost to follow-up
- Study Terminated

If the patient meets the above criteria and discontinues participation in the study, the study completion page of the patient's case report form should be completed.

2.3 Study Endpoints

4

2.4.1 Primary Endpoint

Incidence rates of Major Adverse Events (MAE) within 30 days postoperative

Evaluation time: Within 30 days postoperative

Precautions: Major adverse events are defined as all-cause death, liver failure, intestinal necrosis, splenic infarction, renal infarction, renal failure, cerebral infarction, paraplegia, myocardial infarction, and respiratory failure within 30 Days Postoperative. Among them, liver failure is defined as severe liver damage, leading to serious dysfunction or decompensation of its synthesis, detoxification, excretion and biotransformation. Renal failure is defined as prolonged dialysis, kidney transplantation, or other fatal outcome. Guidance for respiratory failure significantly prolongs intubation, tracheotomy, worsening lung function, oxygen dependence, or other fatal outcome.

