2.4.2 Secondary Endpoint

(1) Immediate intraoperative success rate [Intraoperative]

Definitions of Immediate Technical Success: The delivery system is successfully delivered to the intended location, the thoracoabdominal aortic stent graft system is successfully deployed, the branch vessels are successfully reconstructed, and the delivery system can safely withdraw from the body; No type I or III endoleaks requiring intervention; No conversion surgery.

(2) Perioperative delivery-related complication rate [intraoperative and pre-discharge]

Delivery-related complications refer to intraoperative conveyor-related conversion to laparotomy, bleeding, hematoma, and pseudoaneurysm in the delivery approach

(3) Aneurysm-related mortality rate [6, 12 months postoperation]

Aneurysm-related death is defined as death caused by a ruptured aneurysm or by surgery to treat thoracic and abdominal aortic aneurysm, pararenal abdominal aortic aneurysm.

(4) Incidence rate of Serious Adverse Events (SAEs) [6, 12 months postoperation]

Serious adverse events refers to death or serious deterioration of patient health condition during the clinical trial, including fatal illness or injury, permanent impairment of body structure or function, hospitalization or prolonged hospital stay, and medical or surgical intervention to avoid permanent impairment of body structure or function; Events that cause to fetal distress, fetal death, or congenital abnormalities, congenital defects, etc.

(5) Incidence rate of device-related adverse events [6, 12 months postoperation]

Adverse events refers to adverse medical events that occur during clinical trial, whether or not related to the investigational medical device. However,postoperative stress responses, such as fever,constipation, etc., should be distinguished by the investigator judgment as normal postoperative stress responses and therefore do not need to be recorded as adverse events. Device-related adverse events refers to those that are judged by the investigator to be positively related, possibly related, or undeterminable to the investigational medical device.

(6) Incidence rate of Type I or Type III endoleaks [6 and 12 months postoperation]

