Type I endoleaks, also known as peri-graft endoleaks or graft-related endoleaks, refers to endoleaks formed by the inability of tight-fitting between the stent blood vessels and autologous blood vessels, resulting in continuous blood flowinto the aneurysm lumen, including proximal Type I endoleaks and distal Type I endoleaks. Type III endoleaks refers to the continuous flow of blood into the aneurysm cavity caused by the inability of the stent blood vessel to seal its own interface or the rupture of the artificial vessel.

(7) Incidence rate of Thoracic Abdominal Aortic Stent Graft System Displacement [6, 12 months postoperation]

Stent migration requiring intervention.

(8) Incidence rate of branch stent occlusion [6, 12 months postoperation]

The main stent and branch stent were structurally intact, the blood flow in branch stent was unobstructed, and there was no branch stent occlusion caused by thrombus.

(9) Incidence rate of conversion of thoracic and abdominal aortic aneurysms to open surgery or secondary interventional surgery [6, 12 months postoperation]

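### No endpoint names a survived aneurysm rupture or a new aortic dissection, so a patient with either can be MAE-free at 30 days

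*Combined protocol and SAP*

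**What the plan says.** The primary endpoint (2.4.1) is "Incidence rates of Major Adverse Events (MAE) within 30 days postoperative". Its components are given as a list with no catch-all item: "Major adverse events are defined as all-cause death, liver failure, intestinal necrosis, splenic infarction, renal infarction, renal failure, cerebral infarction, paraplegia, myocardial infarction", followed by respiratory failure. That makes ten components: death from any cause and nine organ or neurological events.

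Section 2.4.2 has nine secondary endpoints. Aneurysm rupture is named in one of them, endpoint (3): "Aneurysm-related death is defined as death caused by a ruptured aneurysm or by surgery to treat thoracic and abdominal aortic aneurysm" (the sentence goes on to include pararenal aneurysm). Three others are broad enough to take in a non-fatal aortic event:

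- SAEs, whose definition includes "hospitalization or prolonged hospital stay, and medical or surgical intervention to avoid permanent impairment of body structure or function";
- device-related AEs, meaning those "judged by the investigator to be positively related, possibly related, or undeterminable to the investigational medical device";
- endpoint (9), "Incidence rate of conversion of thoracic and abdominal aortic aneurysms to open surgery or secondary interventional surgery".

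All three are set at 6 and 12 months. Technical success, judged intraoperatively, also requires "No type I or III endoleaks requiring intervention; No conversion surgery".

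Dissection appears only in the exclusion criteria (2.3.2). Section 3.2.3 plans the MAE incidence and nothing more. Section 3.2.4 lists the secondary rates, none of them for rupture or dissection, and adds that SAE cases will be specifically noted. Section 3.1 gives a sample size of 15 without a calculation.

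**The concern.** The repair is done to stop the aneurysm from rupturing. A 30-day safety endpoint that does not register a survived rupture can describe a patient as free of major events when the treatment has failed in that aim.

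The list is also uneven in severity. Splenic and renal infarction count with no threshold of size or symptoms, so a small infarct seen on imaging makes a patient an MAE case, while a survived aortic rupture does not.

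Because the list is closed, whoever analyses the data cannot repair the omission by interpretation. With 15 patients, one such classification visibly changes the primary result.

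**Working it through.** **Step 1. Set the two events against every endpoint that could capture them.** The events are a survived aneurysm rupture and a survived new aortic dissection, each without any of the ten listed MAEs.

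| Endpoint | Time | Names the event? | Could a survived event count? |
|---|---|---|---|
| MAE (2.4.1) | 30 days | No | No |
| Technical success (2.4.2, 1) | Intraoperative | No | Only if it leads to conversion or prevents a listed success criterion |
| Aneurysm-related death (3) | 6, 12 months | Rupture, if fatal | No |
| SAE (4) | 6, 12 months | No | Yes, ordinarily |
| Device-related AE (5) | 6, 12 months | No | Yes, if judged related, possibly related or undeterminable |
| Type I or III endoleak (6) | 6, 12 months | No | Only if such an endoleak is also present |
| Conversion or reintervention (9) | 6, 12 months | No | Yes, if treated that way |

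The type III endoleak definition does mention rupture of the artificial vessel, but that is a graft defect, not rupture of the aneurysm. The remaining endpoints (delivery-related complications, migration, branch occlusion) name neither event.

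So the events do count in places, but only inside rates that pool other causes, and none of those rates is set at 30 days.

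**Step 2. Size in the primary rate.** The input is n = 15 (3.1). The plan gives no expected rate, performance goal, alpha or power, so there is no figure of its own to reproduce.

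- Change per reclassified patient: 1/15 = 6.7 percentage points.
- The exact (Clopper-Pearson) 95% limits come from beta quantiles: lower B(0.025; x, n−x+1), upper B(0.975; x+1, n−x).

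| MAE patients | Rate | Exact 95% interval |
|---|---|---|
| 0/15 | 0% | 0% to 21.8% |
| 1/15 | 6.7% | 0.2% to 31.9% |
| 2/15 | 13.3% | 1.7% to 40.5% |

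Check on the first row: 1 − 0.025^(1/15) = 0.218. The intervals are added here for scale; the plan states none.

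**Step 3. How likely is it to happen?** Let q be the per-patient probability of the uncounted outcome: a survived rupture or new dissection within 30 days and none of the ten listed events. Assuming independent patients, the chance of at least one among 15 is 1 − (1 − q)^15.

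| Assumed q | Chance of at least one |
|---|---|
| 1% | 14.0% |
| 2% | 26.1% |
| 5% | 53.7% |
| 10% | 79.4% |

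The documents give no value for q, so these rows show only how the result depends on it. They are not estimates.

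**The case against.** **The events are captured elsewhere.** A reader might infer from endpoint (3) that a rupture counts in this trial only if it kills. The documents do not support that. Rupture is *named* only when fatal, but a survived rupture would ordinarily be an SAE, may be a device-related AE and, if treated, counts as conversion or reintervention. Since 3.2.4 has SAE cases specifically noted, a rupture among 15 patients should also be visible as a case. This stands. What is missing is a dedicated rate and a place in the primary endpoint, not the information itself.

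**The likelihood is easy to overstate.** A reader might put an assumed 2% to 5% risk of any survived rupture or dissection into the formula and report a 26% to 54% chance of a misclassified patient. That is not supported either. The documents give no such risk, and a survivor who also has paraplegia, renal failure, respiratory failure or another listed event is already an MAE case. Only survivors with none of the ten are missed, so q is smaller than the overall risk by an unknown amount.

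**The split of endpoints is a legitimate choice.** The MAE composite covers perioperative death and organ injury, with device performance left to the secondary endpoints. This is a feasibility study with no hypothesis or threshold on the MAE rate, so no pass or fail decision can flip. That limits the weight of the point. It does not explain why the event that the repair is meant to prevent has no rate of its own.

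**Dissection is harder to ascertain.** Visit 4 is a telephone contact for patients discharged within 30 days, and the imaging footnote to the data collection table (2.5.2) mentions discharge, 6 months and 12 months. The table's own visit marks could not be read in the copy reviewed. A silent dissection arising after discharge could be missed at day 30 or dated late. This stands, and it argues against placing dissection in the 30-day composite.

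**Conclusion.** The point holds as a gap in endpoint scope. It is neither a contradiction nor a numerical error. No endpoint names non-fatal aneurysm rupture or new aortic dissection, and a survivor of either with none of the ten listed events is MAE-free at 30 days. Each such patient is worth 6.7 percentage points of the primary rate; moving from 0/15 to 1/15 raises the upper exact 95% limit from 21.8% to 31.9%. This assumes that all 15 patients are enrolled and evaluated. How often it would happen cannot be said from the documents.

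The change is worth making because it is cheap and because analysts cannot fill a gap in a closed list. The case is firm for rupture. For dissection it supports a descriptive count only.

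**What to change.** 1. In 2.4.1, add to the MAE list: *new post-procedural aneurysm rupture, fatal or not*. The words new and post-procedural are needed because 2.3.2 excludes a ruptured aneurysm only when the patient is haemodynamically unstable, so a stable rupture may be present at baseline. Fatal ruptures within 30 days already count as deaths; the addition brings in the survivors.
2. In 2.4.2 and 3.2.4, add one descriptive line: the number of patients with new aneurysm rupture (fatal or non-fatal) and, separately, with new aortic dissection found clinically or on scheduled imaging, through 30 days, 6 and 12 months.
3. Leave aneurysm-related death as it is.
4. If patients have already been assessed, keep the present MAE definition as primary and report the expanded MAE and the two counts as labelled additional outcomes.

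Cost: one phrase, one line in each of two sections, a case report form item, and Ethics Committee approval of the amendment (section 4). Adverse event collection already supplies the rupture data, and no sample size calculation or performance goal has to be redone. The downside is that the MAE rate can only stay the same or rise. The dissection count will reflect when the dissection was detected, not necessarily when it began.

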2.5.2 Summary of Trial Data Collection

Visit Time	Visit 1	Visit 2	Visit 3	Visit 4	Visit 5	Visit6
Visit Items	Pre-operation ¹ (-30~0d)	Intra-operat ive (0d)	Before discharge ²	30d Post-operation 2,3 (±3d)	6M±30d Post-operation 2	12M±30d Post-operati on ²
Informed Consent						
Inclusion Exclusion Criteria						
Demographic Data						
Vital Signs						
Current Medical History	A					
Past Medical History	A					
Family Medical History						
Chest and abdomen Examination	A					
Blood routine ⁴						
Urine routine ⁵						
Liver and kidney function ⁶						
Enzyme tests ⁷						
Pregnancy test ⁸						
12-lead ECG						
CTA/MRI ⁹						
DSA						
Surgical Record						
Adverse Events						
Concomitant Medications ¹⁰						
Device Defect						

Summary of Trial Data Collection

1. Preoperative (Visit 1): Preoperative laboratory or imaging studies have been performed prior to the informed consent form and can be used as baseline data

2. Patients requiring staged surgery: 1) Only follow-up visit 3 at the last surgery; 2) Visit 4,5,6 follow-up date calculated from the date of last procedure

3. If discharged within 30 days after surgery, Visit 4 (telephone follow-up) should be completed within 30 days after surgery;

Blood routine test: Hemoglobin content (Hgb), red blood cell count (RBC), white blood cell count (WBC), neutrophil count (NEUT), platelet count (PLT)

Urine routine test: Urine glucose (GLU), urine protein (PRO), urine red blood cell count (ERY), urine white blood cell count (LEU)

6.Liver and kidney function: Aspartate aminotransferase (AST), alanine aminotransferase (ALT), total bilirubin (STB), albumin (ALB), creatinine (SCR), urea (Urea), glucose (GLU) (if glucose values are not included in the liver and kidney function test sheet, the investigator needs to issue a separate test sheet to meet the glucose data collection)

7.Enzymatic tests: Lactate dehydrogenase (LDH), creatine kinase (CK), creatine kinase isoenzyme (CK-MB)

8. Pregnancy test: Only for unmenopausal women

9.1) Patients with abnormal renal function before discharge, 6 months after operation and 12 months after operation were examined by MRI; 2) When collecting the image data of this center, the electronic format is required to be DICOM format, and the distance between each plain scan is recommended to be less than 2 mm.

10. Concomitant medications: Anticoagulants, antiplatelet drugs, antihypertensive drugs, lipid-lowering drugs, glucose-lowering drugs, antibiotics

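### The closed 30-day MAE list omits non-fatal haemorrhagic stroke and does not say whether new paraparesis counts as paraplegia

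*Combined protocol and SAP*

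**What the plan says.** Section 2.4.1 sets the primary endpoint as "Incidence rates of Major Adverse Events (MAE) within 30 days postoperative". The definition opens with "Major adverse events are defined as all-cause death, liver failure" and runs on through "intestinal necrosis, splenic infarction, renal infarction, renal failure, cerebral infarction, paraplegia, myocardial infarction, and respiratory failure within 30 Days Postoperative". That makes ten items, with no wording that would admit others.

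The section then explains three of the ten, starting with "Among them, liver failure is defined as severe liver damage" and going on to renal and respiratory failure. Cerebral infarction and paraplegia get no definition, grade or duration.

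Section 2.4.2 has two wider safety endpoints. One is "Incidence rate of Serious Adverse Events (SAEs) [6, 12 months postoperation"], whose definition includes "permanent impairment of body structure or function, hospitalization or prolonged hospital stay". The other is the rate of device-related adverse events at the same two times, which includes events whose relation to the device cannot be determined. The bleeding named under delivery-related complications is bleeding at the delivery approach, not in the head.

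Section 3.2.3 plans the MAE incidence and nothing by component. Section 3.2.4 plans the secondary rates and says that SAE cases will be specifically noted. Section 3.1 gives a total sample size of 15 with no calculation behind it.

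**The concern.** Stroke and spinal cord injury are major harms to look for after extensive aortic stent-grafting. The plan itself treats spinal cord harm as relevant: the background lists "Reduce spinal cord complications and the mid-stent patency rate is good" among the advantages of endovascular therapy, and there it speaks of spinal cord complications in general, not only of paraplegia.

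The primary endpoint is narrower on both counts. For the brain it names one of the two main types of stroke. For the spinal cord it names one outcome and does not say whether a partial deficit belongs to it. Two patients with comparable disability could therefore be classified differently because of the type of stroke, or because two assessors read an undefined word differently.

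At stake is how the single primary figure of a very small study is read. One patient can decide whether the report shows no major events or one. Any omission works in one direction only: it can lower the MAE rate and cannot raise it.

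**Working it through.** **Inputs.** MAE list and component definitions: section 2.4.1. Other safety endpoints: section 2.4.2. Planned analyses: sections 3.2.3 and 3.2.4. n = 15: section 3.1. The plan assumes no event rate and gives no power calculation, so there is no figure of its own to reproduce.

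**Step 1: apply the list literally.** Take a patient with one neurological event within 30 days and no other listed event.

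| Event | MAE in 2.4.1? | Reason |
|---|---|---|
| Fatal stroke of any type | Yes | All-cause death is an item |
| Non-fatal ischaemic stroke | Yes | Cerebral infarction is an item |
| Non-fatal haemorrhagic stroke | No | No item covers it |
| Paraplegia | Yes | Named |
| New paraparesis | No, or assessor's choice | Not named; paraplegia is not defined |

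**Step 2: look for another passage that widens the list.** There is none. Paraparesis, spinal cord ischaemia, haemorrhagic stroke and intracranial haemorrhage appear nowhere in the document. The SAE and device-related endpoints could capture such events, but they are rates at 6 and 12 months and do not feed the 30-day composite.

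**Step 3: size per patient.** Each patient wrongly left out lowers the rate by 1/n = 1/15 = 6.7 percentage points, provided that the patient has no other listed MAE. If the patient has one, the effect is zero. Exact (Clopper-Pearson) 95% intervals:

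| Rate reported | Rate with one more patient counted |
|---|---|
| 0/15 = 0% (0 to 21.8%) | 1/15 = 6.7% (0.2 to 31.9%) |
| 2/15 = 13.3% (1.7 to 40.5%) | 3/15 = 20.0% (4.3 to 48.1%) |

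For 0/15 the upper limit is 1 − 0.025^(1/15) = 21.8%.

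**Step 4: how likely is at least one such patient?** The documents give no rate, so the per-patient probability p is an assumption. The chance of at least one in 15 is 1 − (1 − p)^15.

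| Assumed p | Chance of at least one in 15 |
|---|---|
| 1% | 14% |
| 2% | 26% |
| 5% | 54% |
| 10% | 79% |

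The range shows only that the outcome depends on p. It is not an estimate for this trial.

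**The case against.** The best counter-argument is that a composite of major events should be strict. Renal failure in section 2.4.1 requires prolonged dialysis, transplantation or a fatal outcome, so leaving out mild or transient leg weakness could be deliberate. This stands in part. How severe a spinal cord deficit must be to count as major is a choice on which reasonable people differ. But the list is not uniformly strict: respiratory failure takes in worsening lung function and oxygen dependence, and splenic and renal infarction carry no severity threshold. Nor does a strict threshold explain why infarction counts and non-fatal haemorrhage does not. Whatever threshold is chosen for the spinal cord, the plan has to state it.

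A reader might also infer three stronger points that the documents do not support.

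- *That these events would reach the results only through the pooled SAE rate.* The device-related adverse event rate is a second route, and section 3.2.4 has SAE cases specifically noted. In 15 patients, such a case that met the SAE definition would probably be visible.
- *That no scheduled assessment records leg function.* The schedule in section 2.5.2 lists "Chest and abdomen Examination" and no neurological examination by name. But most visit marks are missing from the text as read, the same table has a row for adverse events, and the case report form is not among the documents. What is checked, and when, cannot be judged.
- *That the endpoint should test the background statement on spinal cord complications.* That statement compares endovascular with open and hybrid surgery. A single-group study of 15 cannot test it under any MAE definition.

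**Conclusion.** The point holds as a gap in the definition of the primary endpoint. It is firm for non-fatal haemorrhagic stroke, which no item covers. For paraparesis it is a matter of ambiguity: a literal reading excludes it, but an assessor might count a severe case as paraplegia because that term is undefined.

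The consequence is conditional. It is 6.7 points per affected patient, if the event falls within 30 days, the patient has no other listed MAE, and the denominator is the planned 15. It would be wrong to say outright that the 30-day rate understates neurological injury. Only the direction of a possible error is known. The endpoint is also a ten-item composite and does not claim to be a neurological rate. The events would be missing from the primary figure, not necessarily from the trial's safety data.

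The change should be made. It does not affect the sample size.

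**What to change.** 1. In section 2.4.1, replace cerebral infarction with *stroke (ischaemic or haemorrhagic)*.
2. In the same list, replace paraplegia with a graded spinal cord injury item, and state whether persistent paraparesis counts as an MAE. The trial team should choose the threshold and fix it before any outcome is classified.
3. In section 3.2.3, report the number of patients with each MAE component beside the composite. Add a 30-day line for any new lower-limb motor deficit, split into partial or complete and transient or permanent, whether or not it counts in the composite. Readers who prefer another threshold can then apply it.

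The cost is an amendment of wording, matching entries on the case report form where they are not already there, and one additional line in the results. The only downside is that the reported MAE rate may be slightly higher.
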